# 4. OJECTIVE AND ENDPOINTS

	Objective	Endpoint [at 28 days]	Variable			
Primary	•To assess the safety and tolerability of escalating doses of topically applied Bisphosphocin Nu-3 Gel	Treatment emergent events related to clinical investigational product	
 
Vital signs
 
Safety laboratory analysis
 
Local wound/skin assessments
 
Physical examination
 
Adverse events
 
			
Secondary	
 
To assess the clinical effects of Nu-3 on cDFU
 
To assess antimicrobial effects of Nu-3 on wound microflora.
 
To support determination of the appropriate dose range of Nu-3 to be employed in future clinical studies.
 
	
 
Advanced digital imaging wound assessment post debridement
 
Pre and Post debridement digital pictures taken by clinical staff.
 
Changes in wound microbial population pre debridement
 
Recommended Phase 2 Dose (RP2D)
 
	
 
Ulcer surface area
 
Ulcer depth
 
Culture and microflora microbiological analysis
 
			

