# **Assessment of Causality**

- The investigator is obligated to assess the relationship between study treatment and each occurrence of each AE/SAE.
- The investigator will use clinical judgment to determine the relationship.
  - O Unlikely A clinical event, including laboratory test abnormality, with a temporal relationship to drug administration which makes a causal relationship improbable, and in which other drugs, chemicals or underlying disease provide plausible explanations. For the purpose of this protocol, the term unlikely will be considered not related to study medication and an "Adverse Event"
  - O Possible A clinical event, including laboratory test abnormality, with a reasonable time sequence to administrations of the drug, but which could also be explained by concurrent disease or other drugs or chemicals. Information on drug withdrawal may be lacking or unclear. For the purpose of this protocol an event that has possible relationship to study medication will be defined as a "Suspected Adverse Drug Reaction".
  - O Probable A clinical event, including laboratory test abnormality, with a reasonable time sequence to administration of the drug, unlikely to be attributed to concurrent disease or other drugs or chemicals, and which follows a clinically reasonable response on withdrawal. For the purpose of this protocol an event that has probable relationship to study medication will be defined as an "Adverse Drug Reaction".

- Definite This category applies to those AEs which are considered "definitely related" to
  the test drug. The relationship of an AE to study drug may be considered definite, if it
  meets the criteria for "probable" with a definite certainty as to the relationship to the test
  drug.
- Unrelated This category is applicable to those AEs that are judged to be clearly and incontrovertibly due only to extraneous causes (disease, environment, etc.) and do not meet the criteria for drug relationship listed under Unlikely, Possible, Probable, or Definite.
- Alternative causes, such as underlying disease(s), concomitant therapy, and other risk factors, as well as the temporal relationship of the event to study treatment administration will be considered and investigated.
- The investigator will also consult the Investigator's Brochure (IB) and/or Product Information, for marketed products, in his/her assessment.

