# **Analysis**

The following analyses will be conducted:

- Flow chart (subjects) with disposition according to CONSORT criteria. (see shell Figure 1).
- Overall trial statistics (enrollment dates, site numbers, numbers of subjects, group assignments)
- Withdrawals (including death), and loss to follow-up (total and by group assignment) with week of discontinuation and reason.
- Screen failure rate and screen failure reasons according to exclusion criteria

SAP: LLA-Nu3-CLIN002 Page 7 of 21

Demographics between groups at baseline (subject-related and wound-related variables): patient age, smoking/alcohol status, BMI, HbA1c, creatinine levels; diabetes duration); number of concurrent DFUs, prior DFUs and amputations, history of DFU recurrence, history of and significant foot deformities (if available); DFU location, ulcer duration, initial area; baseline variables between groups will be tested using t tests, Mann-Whitney, chi square, and Fisher exact tests (as appropriate) without adjustment for multiplicity testing (see shell Tables 1 and 7).

- Subject comorbidities will be listed using first-level medDRA organ classes by treatment group (see shell Table 8); for each subject the total number of comorbidities will be calculated and then the means between groups will be tested in the same way as for demographics and added to shell Table 1
- Prescription medications will be listed using WHODrug classes by treatment group (see shell Table 9); for each subject the total number of prescription drugs will be calculated and then the means between groups will be tested in the same way as for demographics and added to shell Table 1
- The primary endpoint analysis will be a summary of the incidence of treatmentemergent adverse events (TEAEs), including subject and overall AE rates by treatment group:
  - Summary statistics for each treatment group (count of TEAEs per group/per patient; summary rates per group; notes of unexpected occurrences during the study; relevant decisions made) [text in report]
  - SAE (brief description; resolution; impact on study (e.g., withdrawal, etc.) [text in report]
  - All TEAEs by system organ class (SOC), preferred term (PT), severity, and relationship to test article (see shell Table 10).
- Other safety data will be analyzed as follows:

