Prescription count	XX	XX	XX
{Continue for all subjects.			
Start a new page for every			
additional subject}			

Nu-3: bisphosphocin Nu-3 gel; \*Change from last screening visit

SAP: LLA-Nu3-CLIN002 Page 19 of 21

Shell Table 10. Categorization of AEs by medDRA terms, severity, and relatedness.

TEAE Category	Nu-3 (5%)	Nu-3 (10%)	Placebo
System organ class			
List of classes			
Preferred term(s)	xx (xx)	xx (xx)	xx (xx)
{Continue for all system organ			
classes. Start a new page for each			
new system class as needed}			
Severity			
1	xx (xx)	xx (xx)	xx (xx)
2	xx (xx)	xx (xx)	xx (xx)
3	xx (xx)	xx (xx)	xx (xx)
4	xx (xx)	xx (xx)	xx (xx)
5	xx (xx)	xx (xx)	xx (xx)
Relatedness			
Not related	xx (xx)	xx (xx)	xx (xx)
Unlikely to be related	xx (xx)	xx (xx)	xx (xx)
Possibly related	xx (xx)	xx (xx)	xx (xx)
Probably related	xx (xx)	xx (xx)	xx (xx)
Definitely related	xx (xx)	xx (xx)	xx (xx)
TOTAL	XX	xx	XX

Nu-3: bisphosphocin Nu-3 gel

SAP: LLA-Nu3-CLIN002 Page 20 of 21

Shell Table 11. Microbiological species identification from wound swabs for each subject by treatment group and visit number; randomization visit=1.

Microbiological Identity	Nu-3 (5%)	Nu-3 (10%)	Placebo
Statistic			
Subject ID	XX-XXX	XX-XXX	XX-XXX
Visit 1			
Species 1	text	text	text
{Continue listing for all species			
identified}			
Subject ID	XX-XXX	XX-XXX	XX-XXX
Visit 3			
Species 1	text	text	text
{Continue listing for all species			
identified}			
{Continue for all visits for			
which data are available. Start			
a new page for every subject			
ID}			

Nu-3: bisphosphocin Nu-3 gel

SAP: LLA-Nu3-CLIN002 Page 21 of 21

Shell Table 12. Microbiological susceptibility testing to penicillin, vancomycin, and linezolid from wound swabs for each subject by treatment group and visit number; randomization visit=1.

Susceptibility Testing Statistic	Nu-3 (5%)	Nu-3 (10%)	Placebo
Subject ID	XX-XXX	XX-XXX	XX-XXX
Visit 1			
<penicillin></penicillin>			
Value*	text	text	text
Interpretation**	text	text	text
- <vancomycin></vancomycin>			
Value	text	text	text
Interpretation	text	text	text
<linezolid></linezolid>			
Value	text	text	text
Interpretation	text	text	text
Subject ID	XX-XXX	XX-XXX	XX-XXX
Visit 3			
<penicillin></penicillin>			
Value	text	text	text
interpretation	text	text	text
<vancomycin></vancomycin>			
Value	text	text	text
Interpretation	text	text	text
<linezolid></linezolid>			
Value	text	text	text
Interpretation	text	text	text
{Continue for all visits for			
which data are available. Start			

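### Shell Table 10 gives preferred term, severity and relatedness as separate one-way blocks, so no planned table or listing shows which terms were product-related or how severe the related events were

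*SAP*

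**What the plan says.** Protocol section 4 defines the primary endpoint, at 28 days, as "Treatment emergent events related to clinical investigational product".

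The SAP's Analysis section plans three adverse-event outputs:

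- Report text by group: "count of TEAEs per group/per patient; summary rates per group; notes of unexpected occurrences during the study; relevant decisions made".
- Report text on serious events: "SAE (brief description; resolution; impact on study (e.g., withdrawal, etc.) [text in report".
- One table: "All TEAEs by system organ class (SOC), preferred term (PT), severity, and relationship to test article (see shell Table 10".

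The shell for that table is headed "Shell Table 10. Categorization of AEs by medDRA terms, severity, and relatedness". It has one column each for 5%, 10% and placebo. Its rows run in three consecutive blocks: preferred terms under system organ class, severity 1 to 5, and five relatedness levels. One total follows. The instruction beginning "Continue for all system organ" closes before the severity heading, so it repeats the term rows only. A row such as "Possibly related" has one cell per group, with no breakdown by term or severity.

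The Statistical Analysis part of the Protocol synopsis names the same four attributes for frequency tables and does not ask for them to be crossed. On causality, Protocol Appendix 2 says that "the term unlikely will be considered not related to study medication". It rates intensity as mild, moderate or severe.

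**The concern.** The endpoint is tied to product-related events, so a reader of the final report will ask two things about each dose: what were the related reactions, and how bad were they? Both need joint information (term by relatedness, and severity by relatedness), and Shell Table 10 supplies only the margins. The same printed column can come from a dose whose severe events were all background diabetic illness and from a dose whose severe events were all reactions to the gel.

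Local reactions are the obvious case for a topical product. Local wound and skin assessments are listed among the primary safety variables in Protocol section 4, yet no safety shell reports them. Appendix 2 classes local reactions to the product as adverse events, so among the planned tables they would appear chiefly in Shell Table 10. Shell Table 6 (physical examination changes) is a weak substitute: after screening, the Schedule of Events places the examination only at Visit 8 or early termination, and the minimum system list in section 11.5.1 has no skin item.

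**Working it through.** The plan states no figure on this point, so there is none to reproduce. The check is structural, followed by illustrative arithmetic.

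**1. Is the joint information planned elsewhere?** Of the 12 shell tables, only Shell Table 10 covers adverse events. Shell Tables 3–6, 8, 9, 11 and 12 are subject-level displays of laboratory values, vital signs, physical examination, comorbidities, prescriptions and microbiology. There is no subject-level display of adverse events, no table of related TEAEs by term, and no severity-by-relatedness table. The SAE text covers serious events only, and Appendix 2 (Assessment of Intensity) states that severe and serious are different things.

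**2. What do the margins determine?** For one group, let N be the number of TEAEs, S the number severe and R the number related. The number both severe and related lies between

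max(0, S + R − N) and min(S, R).

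The documents contain no event data, so every count below is assumed. Severe is taken as row 3 or higher, which is also an assumption because the shell's 1–5 rows are not mapped to the Appendix 2 scale.

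| N | S | R | Lower bound | Upper bound |
|---|---|---|---|---|
| 10 | 3 | 4 | max(0, −3) = 0 | min(3, 4) = 3 |
| 12 | 3 | 5 | max(0, −4) = 0 | min(3, 5) = 3 |
| 20 | 4 | 6 | max(0, −10) = 0 | min(4, 6) = 4 |
| 10 | 3 | 8 | max(0, 1) = 1 | min(3, 8) = 3 |

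The bounds coincide only when no event or every event is severe, or no event or every event is related. If 0 < S < N and 0 < R < N, then min(S, R) exceeds both 0 and S + R − N, so the joint count is never fixed. Enumeration agrees: for N = 6, 12, 20 and 30, none of the 25, 121, 361 and 841 such pairs fixes it.

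**3. Two data sets that print identically.** Each has 10 events in one group.

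| Term (events) | Data set A | Data set B |
|---|---|---|
| Application site pain (3) | severity 3, related | severity 1, related |
| Hyperglycaemia (3) | severity 1, not related | severity 3, not related |
| Nausea (2) | severity 1, related | severity 1, related |
| Nausea (2) | severity 1, not related | severity 1, not related |

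Both print terms 3, 3 and 4; severity 7 in row 1 and 3 in row 3; and 5 related, 5 not related. Data set A has 3 severe related events and data set B has 0.

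**4. The same holds for terms.** With 3 application-site-pain events and 5 related events among 10, the number of those pain events that were related lies between max(0, 3 + 5 − 10) = 0 and min(3, 5) = 3.

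**The case against.** Four points can be made for the plan as written.

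- **The endpoint count is readable.** The protocol's endpoint does not mention severity. The relatedness block gives possible, probable and definite counts per dose, and keeps unlikely separate. This stands. A reader might infer that the primary endpoint goes unreported, and that would be wrong. What is missing is the content of the related events.
- **Report text may fill part of the gap.** Severe related events that are also serious will be in the SAE text. The group text includes unexpected occurrences and decisions made. A G3-4 event calls for a treatment pause under the Protocol synopsis and section 12.3.4, and the SAP's Trial Stopping Rules list it too, so such an event could well be mentioned. The SAP's General section also says all collected data will be reported. So the documents do not support saying that a severe, related, non-serious reaction cannot be found in any planned output. They support only that no table or listing guarantees it, since none of these provisions specifies a display.
- **The dose recommendation does not rest on this table.** Under the synopsis (Randomization) and Protocol section 5.9, the DMC reviews all safety data before escalation, against criteria held in its charter, and all data after Cohort 2. This stands, and a reader who infers that the printed margins decide the dose goes beyond the documents.
- **A crossed table may have been intended.** The SAP sentence listing the four attributes is compatible with one. The shell it cites is not, because the continuation instruction ends before the severity block.

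It is also fair to say that this is a small descriptive pilot and that the cross-tabulation could be produced later from data already held. That bears on how serious the gap is, not on whether it exists.

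**Conclusion.** The concern holds as a limit on reporting. If the SAP is followed exactly, the final report gives the number of related TEAEs per dose, but no table or listing shows which preferred terms were related or how severe the related events were. With 12 active subjects planned per dose, a few severe local reactions would matter to a reader, and the planned table could print them exactly as it prints background illness.

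The size of the gap cannot be estimated because the documents give no event data. The range of 0 to 3 severe related events is a property of the assumed margins (3 severe and 4 related of 10), not a forecast. That the margins leave the joint count open does not depend on those counts, apart from the trivial cases above.

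Two further features of the shell add to the difficulty. Its severity rows have no stated correspondence to mild, moderate and severe, and its cells do not say whether subjects or events are counted.

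This is an inexpensive improvement that should be made. It is not a flaw that undermines the trial.

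**What to change.** Revise Shell Table 10 so that, for each system organ class and preferred term and in each treatment group, it gives n (%) of subjects with:

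1. any TEAE;
2. any related TEAE, meaning possible, probable or definite, with unlikely counted as not related as in Appendix 2;
3. related TEAEs by highest severity, each subject counted once per term.

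Keep the one-way severity and relatedness blocks as overall totals, and state whether they count subjects or events. Reconcile the 1–5 severity rows with the mild/moderate/severe scale in Appendix 2, so that the row or rows meaning severe are defined.

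The cost is a shell revision, minor programming and a longer table with many sparse cells. Severity and causality are already assessed for each event under Appendix 2, and TEAEs are already to be MedDRA-coded, so no new data are needed.
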